6.3.3.1 After progression, until death every 3 months (\pm 14 days)

- Survival. (Follow-up can be done by regular visits or phone calls.)
- Quality of life assessment (modified EORTC QLQ C30/BN20) Group A & B only
- Any antitumoral therapy follow-up (Group C only)

6.4 Summary tables

6.4.1 Summary table for Group A

All cycles are 28 days. Cycle 2 will begin 7 days after completion of combination treatment.

GROUP A	Registration		Enrollment	Cycle 1, Day 1 pre-dose	Cycle 1, Days 8, 15	Study Treatment ² Phase		End of treatment ²⁰	Follow Up
	Within 28 days of enrollment ²	Within 14 days of enrollment				Safety / Prescription ¹⁸	Efficacy ¹⁹		
Histological diagnosis of glioblastoma or AA	X								
Signed informed consent	X								
FFPE block or 25 unstained slides sent to [REDACTED]	X								
Medical history, including prior cancer	X								
Determination of MGMT promoter-methylation status			X						
Complete physical examination ³		X						X	
Concomitant medications assessment		X		X	X	X		X	
Steroid dose ⁴		X		X	X	X		X	
Vital signs ⁵		X		X	X	X		X	
Karnofsky Performance Status (KPS) ⁶		X		X	X	X		X	
Hematology ⁷		X		X	X	X		X	
Biochemistry ⁸		X		X	X	X		X	
Coagulation ⁹		X		X		X		X	
Adverse events evaluation ¹⁰				X	X	X		X	

GROUP A (continued)	Registration		Enrollment	Cycle 1, Day 1	Cycle 1, Days 8, 15	Study Treatment Phase		End of treatment ²⁰	Follow Up
	Within 28 days of enrollment ²	Within 14 days of enrollment				Within 7 days of enrollment	Safety / Prescription ¹⁸		
TG02 prescription (+prophylaxis) ¹¹				X		X			
TG02 compliance evaluation ¹¹					X	X		X	
Radiotherapy ¹²				X	X				
12-Lead ECG ¹³		X							
Brain Gd-MRI ¹⁴		X ²					X	X	X ¹⁴
Neurological examination (NANO) ¹⁵		X					X	X	
Quality of life assessment (modified EORTC QLQ C30/BN20) ¹⁶		X					X	X	X ²²
Geriatric evaluation ¹⁷		X							
Optional translational research ²¹		X				X		X	
Survival follow-up ²²									X

¹ Tissue must be sent to [REDACTED] for MGMT analysis as soon as the patient has signed the consent form. Results are needed before enrollment onto the study for Group A.

² Brain Gd-MRI must be completed within 14 days of first dose of TG02. If a 72-hour post-surgery MRI was done and falls within this time window, baseline MRI does not need to be repeated.

³ Complete physical examination will be done at registration and end of study visit. The examination should include any ongoing clinical symptoms. For female patients, menopausal status should be documented.

⁴ For corticosteroids, dose, frequency, dates of administration and route of administration must be recorded in the dedicated eCRF.

⁵ Blood pressure, pulse, temperature, weight and height will be collected at registration. At all other times, blood pressure, pulse, temperature and weight will be collected.

⁶ See Appendix E.

⁷ Hemoglobin, hematocrit, total WBC count with differential (neutrophils and lymphocytes), and platelet count will be measured at registration, Cycle 1 Day 1 pre-dose, Cycle 1 Days 8 and 15, on Day 1 of subsequent cycles, and at the end of study visit. If the registration hematology panel is done within 72 h of pre-dose on Cycle 1 Day 1, it does not need to be repeated.

⁸ Sodium, potassium, chloride, BUN, creatinine, total protein, albumin, AST and/or ALT, total bilirubin, alkaline phosphatase, calcium, magnesium, LDH, glucose, creatinine kinase and phosphate will be measured at registration, Cycle 1 Day 1 pre-dose, Cycle 1 Days 8 and 15, on Day 1 of subsequent cycles, and at the end of study visit. If the registration chemistry panel is done within 72 h of pre-dose on Cycle 1 Day 1, it does not need to be repeated.

⁹ PT, PTT, and INR will be measured at registration, Cycle 1 Day 1 pre-dose and at the end of study visit. If the registration coagulation panel has been done within 72 hours of pre-dose on Cycle 1 Day 1, it does not need to be repeated.

¹⁰ Adverse events grading according to CTCAE 5.0

¹¹ TG02 and RT can start on the day of enrollment but no more than 7 days after enrollment. TG02 is given on Days 1, 4, 8, 11, 15 and 18 of the first cycle in combination with RT. Skipped doses of TG02 will be noted in the patient study drug diary. On days when both TG02 and RT are scheduled, TG02 will be taken approximately 1 hour before RT treatment. TG02 is given on Days 1, 4, 8, 11, 15, 18, 22 and 25 of maintenance cycles. See section 5.2.1.1.

¹² TG02 and RT can start on the day of enrollment but no more than 7 days after enrollment. Standard involved-field radiotherapy (40 Gy in 15 fractions of 2.66 Gy for 3 weeks). See Section 5.7.

¹³ ECG should be repeated if medically indicated.

¹⁴ Brain Gd-MRI will be done every 2 cycles (\pm 8 days) until 6 cycles, then every 3 cycles (\pm 8 days). If treatment is stopped before progression is observed, brain Gd-MRI should be done every 3 months (\pm 14 days). See Appendix J for detailed MRI sequences. Additional details can be found in the study specific imaging guideline.

¹⁵ NANO scale (see section 7.2.4).

¹⁶ QOL evaluation: QLQ C30 and BN20 will be filled out within 2 weeks before enrollment, every 2 cycles until cycle 6 (X 3), every 3 cycles, and at the end of study visit. See Chapter 10 and Appendix F.

¹⁷ G8 screening tool will be completed at registration. See Appendix G.

¹⁸ Safety evaluations in Cycles 2+ should be performed at D1 of each cycle (\pm 3 days)

¹⁹ Efficacy evaluations should be performed every 2 cycles (\pm 8 days) until 6 cycles and then every 3 cycles (\pm 8 days)

²⁰ End of study visit should be performed within 30 days (\pm 5 days) after the last dose of TG02

²¹ Optional collection of 20 mL blood samples for future analysis (baseline, C3D1, progression or end of study)

²² Follow-up for survival and QOL administration every 3 months (\pm 14 days) until death. Follow up can be done by regular visits or phone calls.

6.4.2 Summary table for Group B

Cycle 1 is 35 days including a Day -7 and -4 administration of TG02. All cycles 2+ are 28 days.

GROUP B	Registration		Enrollment	Cycle 1, Day -7	Cycle 1, Days 1, 8, 15, 22	Study Treatment Phase		End of treatment ²⁰	Follow Up
	Within 28 days of enrollment ²	Within 14 days of enrollment		Within 7 days of enrollment		Safety / Prescription ¹⁸	Efficacy ¹⁹		
Histological diagnosis of glioblastoma or AA	X								
Signed informed consent	X								
FFPE block or 25 unstained slides sent to [REDACTED]	X								
Medical history, including prior cancer	X								
Determination of MGMT promoter-methylation status			X						
Complete physical examination ³		X						X	
Concomitant medications assessment		X		X	X	X		X	
Steroid dose ⁴		X		X	X	X		X	
Vital signs ⁵		X		X	X	X		X	
Karnofsky Performance Status (KPS) ⁶		X		X	X	X		X	
Hematology ⁷		X		X	X	X		X	
Biochemistry ⁸		X		X	X	X		X	
Coagulation ⁹		X		X		X		X	

GROUP B (continued)	Registration		Enrollment	Cycle 1, Day -7	Cycle 1, Days 1, 8, 15, 22	Study Treatment Phase		End of treatment ²⁰	Follow Up
	Within 28 days of enrollment ²	Within 14 days of enrollment		Within 7 days of enrollment		Safety / Prescription ¹⁸	Efficacy ¹⁹		
Adverse events evaluation ¹⁰				X	X	X		X	
TG02 prescription (+prophylaxis) ¹¹				X		X			
TG02 compliance evaluation ¹¹					X	X		X	
TMZ prescription (+ prophylaxis) ¹²				X					
TMZ compliance evaluation ¹²					X	X		X	
12-Lead ECG ¹³		X							
Brain Gd-MRI ¹⁴		X ²					X	X	X ¹⁴
Neurological examination (NANO) ¹⁵		X					X	X	
Quality of life assessment (modified EORTC QLQ C30/BN20) ¹⁶		X					X	X	X ²²
Geriatric evaluation ¹⁷		X							
Optional translational research ²¹		X				X		X	
Survival follow-up ²²									X

¹ Tissue must be sent to [REDACTED] for MGMT analysis as soon as the patient has signed the consent form. Results are needed before enrollment onto the study for Group B.

² Brain Gd-MRI must be completed within 14 days of first dose of TG02. If a 72-hour post-surgery MRI was done and falls within this time window, baseline MRI does not need to be repeated.

³ Complete physical examination will be done at registration and end of study visit. The examination should include any ongoing clinical symptoms. For female patients, menopausal status should be documented.

⁴ For corticosteroids, dose, frequency, dates of administration and route of administration must be recorded in the dedicated eCRF.

⁵ Blood pressure, pulse, temperature, weight and height will be collected at registration. At all other times, blood pressure, pulse, temperature and weight will be collected.

⁶ See Appendix E.

⁷ Hemoglobin, hematocrit, total WBC count with differential (neutrophils and lymphocytes), and platelet count will be measured at registration, Cycle 1 Day 1 pre-dose, Cycle 1 Days 8 and 15, on Day 1 of subsequent cycles, and at the end of study visit. If the registration hematology panel is done within 72 h of pre-dose on Cycle 1 Day 1, it does not need to be repeated.

⁸ Sodium, potassium, chloride, BUN, creatinine, total protein, albumin, AST and/or ALT, total bilirubin, alkaline phosphatase, calcium, magnesium, LDH, glucose, creatinine kinase and phosphate will be measured at registration, Cycle 1 Day 1 pre-dose, Cycle 1 Days 8 and 15, on Day 1 of subsequent cycles, and at the end of study visit. If the registration chemistry panel is done within 72 h of pre-dose on Cycle 1 Day 1, it does not need to be repeated.

⁹ PT, PTT, and INR will be measured at registration, Cycle 1 Day 1 pre-dose and at the end of study visit. If the registration coagulation panel has been done within 72 hours of pre-dose on Cycle 1 Day 1, it does not need to be repeated.

¹⁰ Adverse events grading according to CTCAE 5.0

¹¹ TG02 (Day -7) can start on the day of enrollment but no more than 7 days after enrollment. TG02 is given on Days -7 and -4 prior to the first cycle. TG02 is given on Days 1, 4, 22 and 25 of each cycle.

¹² TMZ prescription: d1 to d5 of every cycle (max 12 cycles). On days when both TG02 and TMZ are administered, TG02 will be administered first, 1 hour before TMZ.

¹³ ECG should be repeated if medically indicated.

¹⁴ Brain Gd-MRI will be done every 2 cycles (\pm 8 days) until 6 cycles, then every 3 cycles (\pm 8 days). If treatment is stopped before progression is observed, brain Gd-MRI should be done every 3 months (\pm 14 days). See Appendix J for detailed MRI sequences. Additional details can be found in the study specific imaging guideline.

¹⁵ NANO scale (see section 7.2.4).

¹⁶ QOL evaluation: QLQ C30 and BN20 will be filled out within 2 weeks before enrollment, every 2 cycles until cycle 6 (X 3), every 3 cycles, and at the end of study visit. See Chapter 10 and Appendix F.

¹⁷ G8 screening tool will be completed at registration. See Appendix G.

¹⁸ Safety evaluations in Cycles 2+ should be performed at D1 of each cycle (\pm 3 days)

¹⁹ Efficacy evaluations should be performed every 2 cycles (\pm 8 days) until 6 cycles and then every 3 cycles (\pm 8 days)

²⁰ End of study visit should be performed within 30 days (\pm 5 days) after the last dose of TG02

²¹ Optional collection of 20 mL blood samples for future analysis (baseline, C3D1, progression or end of study)

²² Follow-up for survival and QOL administration every 3 months (\pm 14 days) until death. Follow up can be done by regular visits or phone calls.

6.4.3 Summary table for Group C

All cycles are 28 days.

GROUP C	Registration	Cycle 1, Day 1	Cycle 1, Days 8, 15, 22 ⁹	Study Treatment Phase		End of treatment ¹⁵	Follow Up
	Within 14 days of first dose of TG02			Safety / Prescription ¹³	Efficacy ¹⁴		
Histological diagnosis of glioblastoma or AA	X						
Online registration FFPE block or 25 unstained slides from surgery at diagnosis of GBM/AA to be sent to Department of Neurology, University Hospital Zurich	X						
Signed informed consent	X						
Medical history, including prior cancer	X						
Complete physical examination ¹	X					X	
Concomitant medications assessment	X	X	X	X		X	
Steroid dose ²	X	X	X	X		X	
Vital signs ³	X	X	X	X		X	
Karnofsky Performance Status (KPS) ⁴	X	X	X	X		X	
Hematology ⁵	X	X	X			X	
Biochemistry ⁶	X	X	X			X	
Coagulation ⁷	X	X		X		X	
Serum or urine pregnancy test ⁸	X			X		X	
Adverse events evaluation ¹⁰		X	X	X		X	

GROUP C (continued)	Registration	Cycle 1, Day 1	Cycle 1, Days 8, 15, 22 ⁹	Study Treatment Phase		End of treatment ¹⁷	Follow Up
	Within 14 days of first dose of TG02			Safety / Prescription ¹⁵	Efficacy ¹⁶		
TG02 prescription (+prophylaxis) ¹¹		X		X			
TG02 compliance evaluation ¹¹			X	X		X	
12-Lead ECG ¹²	X						
Brain Gd-MRI ¹³	X				X	X	X ¹³
Neurological examination (NANO) ¹⁴	X				X	X	
Optional translational research ¹⁸	X			X		X	
Survival follow-up ¹⁹							X
Optional TG02 PK sampling		X ²⁰	X ²¹				

¹ Complete physical examination will be done at registration and end of study visit. Examination should include any ongoing clinical symptoms. For female patients, menopausal status should be documented.

² For corticosteroids, dose, frequency, dates of administration and route of administration must be recorded in the dedicated eCRF.

³ Blood pressure, pulse, temperature, weight and height will be collected at registration. At all other times, blood pressure, pulse, temperature and weight will be collected.

⁴ See Appendix E.

⁵ Hemoglobin, hematocrit, total WBC count with differential (neutrophils and lymphocytes), and platelet count will be measured at registration, Cycle 1 Day 1 pre-dose, Cycle 1 Days 8, 15 and 22, on Day 1 of subsequent cycles, and at the end of study visit. If the registration hematology panel is done within 72 h of pre-dose on Cycle 1 Day 1, it does not need to be repeated.

⁶ Sodium, potassium, chloride, BUN, creatinine, total protein, albumin, AST and/or ALT, total bilirubin, alkaline phosphatase, calcium, magnesium, LDH, glucose, creatinine kinase and phosphate will be measured at registration, Cycle 1 Day 1 pre-dose, Cycle 1 Days 8, 15 and 22, on Day 1 of subsequent cycles, and at the end of study visit. If the registration chemistry panel is done within 72 h of pre-dose on Cycle 1 Day 1, it does not need to be repeated.

⁷ PT, PTT, and INR will be measured at registration, Cycle 1 Day 1 pre-dose and at the end of study visit. If the registration coagulation panel has been done within 72 hours of pre-dose on Cycle 1 Day 1, it does not need to be repeated.

⁸ For WOCBP, serum or urine pregnancy test will be conducted within 72 hours prior to the first dose of TG02, D1 of every cycle and at end of study visit.

⁹ If no SAEs are reported by the patient or ongoing on Day 8, the safety evaluations on Days 15 and 22 can be omitted.

¹⁰ Adverse events grading according to CTCAE 5.0

¹¹ TG02 should start within 7 days of registration. TG02 will be taken on days 1, 4, 8, 11, 15, 18, 22 and 25 in all cycles. Skipped doses of TG02 will be noted in the patient study drug diary. See section 5.2.1.3.

¹² ECG should be repeated if medically indicated.

¹³ Baseline brain Gd-MRI must be completed within 14 days of first dose of TG02. For patients with surgery for recurrence, if a 72-hour post-surgery MRI was done and falls within this time window, baseline MRI does not need to be repeated. Brain Gd-MRI will also be every 2 cycles (\pm 8 days) until 6 cycles, then every 3 cycles (\pm 8 days). If treatment is stopped

before progression is observed, brain Gd-MRI should be done every 3 months (\pm 14 days). See Appendix J for detailed MRI sequences. Additional details can be found in the study specific imaging guideline.

¹⁴ See section 7.2.4.

¹⁵ Safety evaluations in Cycles 2+ should be performed at D1 of each cycle (\pm 3 days)

¹⁶ Efficacy evaluations should be performed every 2 cycles (\pm 8 days) until 6 cycles and then every 3 cycles (\pm 8 days)

¹⁷ End of study visit should be performed within 30 days (\pm 5 days) after the last dose of TG02

¹⁸ Optional collection of 20 mL blood samples for future analysis (baseline, C3D1, progression or end of study)

¹⁹ Follow-up for survival every 3 months (\pm 14 days) and new anti-tumoral therapy information until death. Follow up can be done by regular visits or phone calls.

²⁰ TG02 PK sample will be collected at Cycle1D1 pre-dosing only.

²¹ TG02 blood samples will be collected at Cycle 1 day 15 only: pre- dose and 30 min, 1 hr, 2hrs, 4 hrs, 8 hrs and 24 hrs post-dose of TG02.

²²

7 Criteria of evaluation

7.1 Study procedures

7.1.1 Compliance evaluation

TG02 (all groups) and TMZ (group B) compliance will be verified by:

- (1) a patient diary. Treatment intake, dose modifications, skipped doses of TG02 and delays/interruptions of TMZ will be recorded in the patient diary and reported on the CRF.
- (2) capsule counts at each visit, with the number of capsules taken relative to the number expected to be taken summarized for each cycle. The patient must take $\geq 75\%$ of the planned doses of TG02 in a cycle to be deemed compliant. Planned dose interruptions may occur and will not result in a patient being considered as noncompliant. A patient will be considered noncompliant if he/she is judged by the investigator to have intentionally or repeatedly taken $\geq 125\%$ of the planned doses of TG02 in a cycle.

Patients will be instructed to bring all unused capsules and their medication diary to each study visit for assessment of compliance.

7.1.2 Physical examination

Physical examination will be performed as per local standard practice.

7.1.3 Neurological examination

Neurological examination will be performed using the NANO scale (section 7.2.4, Appendix I). A conclusion on the evaluation of neurological status (improved, stable, and deteriorated) by the treating physician is required at each evaluation.

At any time, in case of suspicion of progression, a brain MRI should be done.

7.1.4 Karnofsky Performance Score

Karnofsky Performance Status will be determined according to the scale provided in Appendix E.

7.1.5 Quality of life assessment

A modified version of the QLQ C30 and BN20 questionnaires will be used to assess the quality of life. (See chapter 10 and Appendix F).

7.1.6 Geriatric assessment

See section 7.4 and Appendix G.

7.1.7 Blood analysis

Blood analysis can be done as per local standard practice, at the hospital laboratory during a hospitalization or at the local laboratory. Laboratory reference range values have to be provided for all the laboratories used by the patients.

7.1.8 Magnetic resonance imaging (MRI)

The basic MRI protocol is mandatory for all participating centers for baseline and follow-up MRI examinations. The order of the prescribed sequences particularly after contrast administration should be respected across all visits for each patient during the treatment. The duration of MRI data acquisition is 30 minutes. According to the preferences of the respective centers, further sequences can be added to the protocol. Only 1.5T and 3T MR scanners should be used. All scans should be sent to EORTC HQ for central review. Details on how to do this can be found in the study specific imaging guidelines.

Detailed acquisition parameters are provided in the study specific guidelines.

If progression is not clear (e.g. pseudo progression), it is recommended to continue study treatment and confirm the diagnosis of progression with a new MRI, including perfusion sequences, no earlier than 28 days later.

Table 1: Overview of the required study time points

	Baseline	During treatment	End of study
Group A	Within 14 days of first dose of TG02 ¹	Every 2 cycles (\pm 8 days) until 6 cycles (X 3 times) then every 3 cycles (\pm 8 days)	Within 30 days (+/- 5 days) of last dose of TG02
Group B	Within 14 days of first dose of TG02 ¹	Every 2 cycles (\pm 8 days) until 6 cycles (X 3 times) then every 3 cycles (\pm 8 days)	Within 30 days (+/- 5 days) of last dose of TG02
Group C	Within 14 days prior to first dose of study treatment ²	Every 2 cycles (\pm 8 days) until 6 cycles (X 3 times) then every 3 cycles (\pm 8 days)	Within 30 days (+/- 5 days) of last dose of TG02

¹ If a 72-hour post-surgery MRI was done and falls within this time window, baseline MRI does not need to be repeated.

² For non-surgical patients, baseline brain Gd-MRI must be completed within 14 days of first dose of TG02. For patients with surgery for recurrence, if a 72-hour post-surgery MRI was done and falls within this time window, baseline MRI does not need to be repeated.

7.1.9 MGMT promoter methylation (for Groups A and B)

MGMT promoter methylation status will be centrally assessed in groups A and B by methylation-specific PCR at [REDACTED].

Tissue samples in groups A and B must be sent to [REDACTED] as soon as the patient has signed the consent form to avoid any delay in the treatment. Guidelines for human biological management will be provided in a separate document.

7.1.10 IDH1^{R132H} mutation

IDH1^{R132H} mutation will be determined locally by immunohistochemistry.

In patients older than 55 years of age at diagnosis with a histologically typical glioblastoma, without a pre-existing lower grade glioma and with non-midline tumor location, immunohistochemical negativity for IDH1^{R132H} suffices for classification as glioblastoma, IDH-wild-type (Ref. 16, Ref. 35).

In all other instances of diffuse gliomas, lack of IDH1^{R132H} immunopositivity should be followed by IDH1 and IDH2 sequencing to detect or exclude other less common IDH mutations.

7.1.11 Other pathological and molecular examinations in anaplastic astrocytoma

IDH mutation and loss of nuclear ATRX expression suffice for classification as IDH-mutant astrocytic gliomas.

ATRX expression should be explored by immunohistochemistry.

IDH-wild-type diffuse astrocytic gliomas with loss of nuclear ATRX expression may be additionally tested for histone 3 mutations (immunostaining for histone 3 K27M (H3-K27M) mutation) according to EANO guidelines (Ref. 35).

7.2 Criteria of Evaluation

7.2.1 Safety

See section 7.3 evaluation of safety.

7.2.2 Efficacy

To ensure a homogeneous radiological evaluation, all MRI images will be retrospectively centrally reviewed.

The following criteria will be used to determine the efficacy of study treatment.

Progression Free Survival (PFS): PFS is defined as the number of days from consent to the date of earliest disease progression based on Response Assessment in Neuro Oncology (RANO) criteria (as determined by the Investigator) or to the date of death, if disease progression does not occur. In group C, patients for whom neither death nor progression have been documented will be censored on the date of the last radiological assessment if they have no post anti-cancer therapy. If a patient has other post anti-cancer therapy prior to progression or death, the data will be censored at the date of last radiological assessment prior to or on the start date of post anti-cancer therapy. In group A and B, post anti-cancer therapy is not collected. The data will be censored at the date of the last radiological assessment. In all groups, if a patient with no post-baseline radiological assessment did not experience progression nor died, then the data will be censored at the date of enrollment.

PFS at 6 months (PFS-6) is the PFS rate at 6 months extracted from the PFS Kaplan Meier distribution based on RANO criteria (as determined by the Investigator)

Overall Survival (OS): OS is defined as the number of days from consent to the date of death due to any cause. If a patient has not died, the data will be censored at the last date documented to be alive.

OS at 9 months (OS-9) is the OS rate at 9 months extracted from the OS Kaplan Meier distribution.

Objective (ORR) and complete (CR) response rates are the proportions of patients with best overall response PR+CR or CR (see below) respectively.

Duration of objective (complete) response (DOR): DOR is determined as the number of days from the time point where the overall response PR or CR (CR) was first seen to the earliest date of detection of disease progression based on RANO criteria (as determined by the Investigator) or to the date of death, if disease progression does not occur. The same censoring rules defined above for PFS are applicable.

A success is defined as a patient achieving either confirmed CR or PR (> 4 week) or free of progression at 6 months.

Neurologic progression free survival (NPFS): NPFS is defined as the number of days from patient enrollment in trial until the date of first neurologic progression or the date of patient's death whichever occurs first, regardless of whether radiological progression has occurred or not. If a patient neither experienced neurologic progression nor died, then the data will be censored at the last date of post-baseline neurologic assessment. If a patient with no post-baseline neurologic assessment did not experience neurologic progression nor died, then the data will be censored at the date of enrollment.

Clinical deterioration free survival (CDFS): CDFS is defined as the number of days from patient enrollment in trial until the date of first clinical deterioration or the date of patient's death whichever occurs first, regardless of whether clinical deterioration has occurred or not. If a patient neither experienced clinical deterioration nor died, then the data will be censored at the last date of post-baseline Karnofsky performance score assessment. If a patient with no post-baseline Karnofsky performance score assessment did not experience clinical deterioration nor died, then the data will be censored at the date of enrollment.

See definitions below.

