5.2 Initial dose and schedule

5.2.1 Study Drug Administration

Patients are registered to the study when they sign the PISIC. For groups A and B, patients must have a central assessment of MGMT testing after registration. Once MGMT status is confirmed, the site is informed by a notification e-mail, and proceeds to the next step to enroll the patient into either group A or group B. Please see section 13.1.2 for detailed information.

Dosing calendars can be found in Appendix H.

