6.1 Before treatment start

6.1.1 Registration

6.1.1.1 Groups A and B

These assessments must be completed within 28 days prior to enrollment

- Histological diagnosis of glioblastoma or anaplastic astrocytoma
- Informed consent for phase 1b
- FFPE block or 25 unstained slides. The slides or the block MUST be sent to [REDACTED] [REDACTED] for MGMT analysis as soon as the patient has signed the consent form. Results are needed before enrollment onto the study for these two groups (for more information see sections 7.1.9, 13.1.2 and HBM guidelines provided as separate document).
- Evaluation of inclusion and exclusion criteria
- Medical history, including prior cancer

These assessments must be completed within 14 days of enrollment

- Complete physical examination, including any ongoing clinical symptoms. For female patients, menopausal status should be documented.
- Concomitant medications assessment
- Steroid dose. For corticosteroids, dose, frequency, dates of administration and route of administration must be recorded in the dedicated eCRF.
- Vital signs: blood pressure, pulse, temperature, weight, height
- Karnofsky Performance Status (KPS) (see Appendix E)
- Hematology: hemoglobin, hematocrit, total WBC count with differential (neutrophils and lymphocytes), and platelet count
- Biochemistry: sodium, potassium, chloride, BUN, creatinine, total protein, albumin, AST, ALT, total bilirubin, alkaline phosphatase, calcium, magnesium, LDH, glucose, creatinine kinase and phosphate
- Coagulation: PT, PTT and INR
- Complete neurological examination (NANO, see section 7.2.4)
- Quality of life assessment (modified EORTC QLQ C30/BN20) (see Chapter 10 and Appendix F)
- Geriatric evaluation (G8) (see Appendix G)
- 12-Lead ECG

This assessment must be scheduled within 14 days of first dose of TG02

- Brain gadolinium (Gd)-MRI. If a 72-h post-surgery MRI was done and falls within this time window, baseline MRI does not need to be repeated. See Section 7.2.5 and Appendix J for detailed MRI sequences. Additional information can be found in the study specific imaging guidelines.

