6.1.1.2 Group C

These assessments must be completed within 14 days of first dose of TG02

- Histological diagnosis of glioblastoma or anaplastic astrocytoma
- Informed consent
- Online registration of FFPE block or 25 unstained slides from the surgery at glioblastoma diagnosis (for more information see section 14.3 and HBM guidelines provided as separate document)
- Evaluation of inclusion and exclusion criteria

- Medical history, including prior cancer
- Complete physical examination, including any ongoing clinical symptoms. For female patients, menopausal status should be documented.
- Concomitant medications assessment
- Steroid dose. For corticosteroids, dose, frequency, dates of administration and route of administration must be recorded in the dedicated eCRF.
- Vital signs: blood pressure, pulse, temperature, weight, height
- Karnofsky Performance Status (KPS) (see Appendix E)
- Hematology: hemoglobin, hematocrit, total WBC count with differential (neutrophils and lymphocytes), and platelet count
- Biochemistry: sodium, potassium, chloride, BUN, creatinine, total protein, albumin, AST, ALT, total bilirubin, alkaline phosphatase, calcium, magnesium, LDH, glucose, creatinine kinase and phosphate
- Coagulation: PT, PTT and INR
- 12-Lead ECG
- Brain gadolinium (Gd)-MRI: baseline must be completed within 14 days of first dose of TG02. For patients with surgery for recurrence, if a 72-hour post-surgery MRI was done and falls within this time window, baseline MRI does not need to be repeated. See Appendix J for detailed MRI sequences. Additional information can be found in the study specific imaging guidelines. The last brain MRI before disease progression diagnosis should also be available.
- Complete neurological examination (NANO, see section 7.2.4)

This assessment must be completed within 72 hours of first dose of TG02

- For WOCBP, serum or urine pregnancy test within 72 hours prior to the first dose of TG02

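### In Groups A and B, PFS and OS are counted from consent although patients enter the analysis only after enrolment and a first TG02 dose, so the consent-to-enrolment wait (up to 28 days) is guaranteed event-free time

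*Combined protocol and SAP*

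**What the plan says.** **Time origin.** Section 7.2.2 gives "PFS is defined as the number of days from consent to the date of earliest disease progression" and "OS is defined as the number of days from consent to the date of death due to any cause". The same section uses enrolment elsewhere. A patient with no post-baseline scan who "did not experience progression nor died, then the data will be censored at the date of enrollment" has enrolment as the censoring date. The two Group C endpoints also start there: "NPFS is defined as the number of days from patient enrollment in trial until the date of first neurologic progression" and "CDFS is defined as the number of days from patient enrollment in trial until the date of first clinical deterioration".

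**From consent to enrolment, Groups A and B.** Section 5.2.1: "Patients are registered to the study when they sign the PISIC". Section 6.1.1.1 includes informed consent in a list headed "These assessments must be completed within 28 days prior to enrollment". Section 13.1.2 expects the central MGMT result within 14 days of tissue arrival and, in the dose-limiting-toxicity phase, allows a wait of up to 4 weeks before enrolment. Section 6.1.2 allows enrolment only once the MGMT status is known and if general and neurological status is still stable. Sections 6.1.3.1 and 6.1.3.2 then allow up to 7 days to first treatment.

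**Who is analysed.** Section 8.2.2 runs all Group A/B analyses, including PFS-6, OS-9 and the medians, in the safety population. Section 8.2.1 defines this as patients with at least one TG02 dose who were not replaced. The intention-to-treat set in 8.2.1 is also limited to enrolled patients.

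**Group C.** Section 6.1.2 places registration and enrolment at the signing of consent.

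**The concern.** The clock starts before the patient can qualify for the analysis. A Group A or B patient who dies or deteriorates while waiting for the MGMT result or for a cohort slot is never enrolled and appears in no analysis set. A patient who gets through the wait has it credited as survival time. This is immortal-time bias, and it acts in one direction only.

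For OS the guarantee is strict: a patient must be alive to be enrolled and dosed. For PFS it is nearly strict. Enrolment requires clinical stability, and radiological progression is judged against a baseline MRI taken within 14 days of the first TG02 dose.

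At stake are the Group A/B efficacy estimates. Part of what they report would be laboratory turnaround and queueing rather than treatment, and the planned confidence intervals do not reflect it.

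**Working it through.** The plan states no target or expected PFS or OS rate for Groups A and B, so there is no figure of its own to reproduce. The size has to be illustrated under an assumption.

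**Inputs**
- Lag d from consent to enrolment: 7, 14 and 28 days. The maximum of 28 is from 6.1.1.1; 7 and 14 are assumed. The documents do not give the actual distribution.
- Medians m: 3.9 months (PFS) and 7.6 months (OS), the radiotherapy-alone arm of the elderly trial described in section 1.1. The combined arm's 5.2 and 9.3 months serve as a second case.
- Assumption: exponential survival from enrolment, with no event possible during the lag. One month = 30.44 days.

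**Formulas**
- True rate at landmark L: S(L) = 0.5^(L/m).
- Rate read from consent: S(L − d/30.44).
- Median read from consent: m + d/30.44.

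**PFS-6, m = 3.9.** True: 0.5^(6/3.9) = 34.4%.
- d = 7: 0.5^(5.77/3.9) = 35.9% (+1.4)
- d = 14: 0.5^(5.54/3.9) = 37.4% (+2.9)
- d = 28: 0.5^(5.08/3.9) = 40.5% (+6.1)

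**OS-9, m = 7.6.** True: 0.5^(9/7.6) = 44.0%.
- d = 7: 0.5^(8.77/7.6) = 44.9% (+0.9)
- d = 14: 0.5^(8.54/7.6) = 45.9% (+1.9)
- d = 28: 0.5^(8.08/7.6) = 47.9% (+3.9)

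(Differences are taken before rounding.)

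**Medians.** They rise by 7/30.44 = 0.2, 14/30.44 = 0.5 and 28/30.44 = 0.9 month.

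**Second case.** With m = 5.2 and 9.3, the 28-day shifts are +5.9 points (44.9% to 50.8%) for PFS-6 and +3.6 points (51.1% to 54.8%, before rounding) for OS-9. The result depends little on which pair of medians is used.

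**Sampling error for comparison.** 1.96 × √(0.344 × 0.656/n) is 19.0 points at n = 24 (Group A) and 26.9 points at n = 12 (Group B).

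**How far the lag can reach.** Section 5.7 wants radiotherapy to start within 6 weeks (42 days) of surgery, on the day of the first TG02 dose. A Group A patient at both the 28-day and the 7-day limits would have to consent within 42 − 28 − 7 = 7 days of surgery. Twenty-eight days is therefore an edge case in Group A.

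**A conflict found on the way.** A 14-day MGMT turnaround plus a 4-week wait is 14 + 28 = 42 days, before any shipping time. That exceeds the 28-day window in 6.1.1.1, and the documents do not say what happens then.

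**The case against.** The strongest reply is that little depends on these estimates. Section 8.1.1 calls Groups A and B exploratory, with feasibility as the prime goal, and 8.2.2 plans descriptive analysis without formal inference. No comparator, threshold or go/no-go rule is attached to their PFS or OS. The 4-week wait applies only during escalation, which takes at most 12 patients per group (6 at each of two dose levels). For the others, shipping plus an MGMT result expected within 14 days makes a shift of about 3 points in PFS-6 and 2 in OS-9 more plausible than the maximum. All of this stands. It limits the importance of the point but does not remove a one-directional error.

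Four stronger readings are tempting, and the documents do not support them.

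- *That the Group C primary endpoint is inflated.* A reader might infer a lag from 6.1.1.2, which lists consent under "These assessments must be completed within 14 days of first dose of TG02", and from 13.2.1, which records the consent date as its own field. But 6.1.2 says that Group C enrolment occurs at consent, and 6.1.3.3 allows at most 7 days from registration to first dose. The 14 days is an outer window for a list of assessments. An inflated error rate would require patients to depart from 6.1.2.
- *That Groups A and B already have endpoints timed from enrolment.* Section 2.2.2 lists NPFS and CDFS for Group C only. They show that 7.2.2 uses two origins, not that Group A/B endpoints conflict with each other.
- *That the lag pushes the cycle 6 MRI past month 6 and so hides progressions.* Deaths and clinical progression between scans count as events, and the ±8-day scan window alone can move the scan across the landmark. This is mainly a separate scheduling matter.
- *That the cycle 1 replacement rule belongs to the same bias.* It is a different selection, which changing the origin does not touch. Section 8.2.2 reports the efficacy data of patients outside the safety population separately.

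**Conclusion.** The point holds for Groups A and B. Counting from consent while analysing only patients who reached enrolment and treatment overstates median PFS, PFS-6, median OS and OS-9. Under exponential survival with the section 1.1 medians, the overstatement is 1.4 to 6.1 points for PFS-6, 0.9 to 3.9 points for OS-9 and 0.2 to 0.9 month for the medians, over lags of 7 to 28 days. The upper end requires every patient to be at the protocol maximum.

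The medians come from patients considered eligible for combined treatment, which Group A/B patients are not, so the sizes are illustrative. The direction does not depend on them. For scale, the OS gain cited in section 1.1 is 1.7 months (7.6 to 9.3).

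The shift is well inside sampling error, concerns secondary and descriptive endpoints, and leaves the MTD and the recommended phase II dose untouched. Group C is unaffected, given 6.1.2. The change should be made because it is cheap and removes a systematic error, not because a trial conclusion depends on it.

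**What to change.** 1. In 7.2.2, define PFS and OS from the date of enrolment instead of from consent. This matches the censoring date already used there for unscanned patients and the origin used for the Group C endpoints NPFS and CDFS. In Group C it changes nothing where the two dates coincide, as 6.1.2 provides.
2. In 8.2.2, state what the edit leaves in place: up to 7 days between enrolment and first dose (by the same arithmetic, up to +1.4 points in PFS-6 and +0.9 in OS-9), and the exclusion from the main Group A/B estimates of patients replaced during cycle 1 (8.1.1, 8.2.1).
3. Reconcile the 28-day window in 6.1.1.1 with the 14-day MGMT turnaround plus wait of up to 4 weeks in 13.1.2.

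The cost is one phrase in two definitions, a short statement in 8.2.2 and one reconciliation. No data are needed beyond the consent and enrolment dates. The downside is that each Group A/B patient's PFS and OS times shorten by that patient's own lag, 0 to 28 days under 6.1.1.1, so the reported medians will be lower.
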